| Visit  | 1                      | 2         | 3      | 4      | 5      | 6         |                            |  |   |                               |
| Day/Week   | Day -28 to -7          | Day 1     | Week 2 | Week 4 | Week 6 | Week 8    | -                          | -  | Week 6  |                               |
| Visit window (days) b   | -28 to -7              | NA        | ±3     | ±3     | ±3     | ±3        | -                          | -  | ±3  |                               |
| Classification of SLE (ACR endorsed criteria, 1997)                          | X                      |           |        |        |        |           |                            |  | 11.2.5  |                               |
| CLASI and RCLASI e  | X                      | (X)       |        |        |        |           |                            |  | 11.2.6, 11.2.7                                      |                               |
| Identification of target lesions b                                | X                      | X         |        |        |        |           |                            |  | 11.2.8  |                               |
| Subject assessments of efficacy and health-related quality of life    |                        |           |        |        |        |           |                            |  |   |                               |
| DLQI   |                        | X         |        |        |        |           |                            |  |   | 11.6.1.2                      |
| PaGA   | X                      | X         | X      | X      | X      | X         |                            | X  |   | 11.6.1.1                      |
| Investigator assessments of efficacyi                      |                        |           |        |        |        |           |                            |  |   |                               |
| IGA  | X                      | X         | X      | X      | X      | X         |                            | X  | X   | 11.3.1                        |
| Skin lesion activity (erythema, scaling/hyperkeratosis, oedema/infiltration) | X                      | X         | X      | X      | X      | X         |                            | X  |   | 11.3.2                        |

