- a) Subjects that fail to meet all eligibility criteria at screening may be re-assessed for eligibility at a later stage under certain circumstances (see Section 8.4). For these subjects, re-assessment of eligibility will be performed at an additional screening visit prior to baseline (Day 1).
- b) If the date of a trial visit does not conform to the clinical trial protocol, subsequent visits should be planned to maintain the visit schedule relative to baseline.
- c) Subjects who discontinue IMP or withdraw from the trial will be asked to return to the trial site for an early termination visit as soon as possible after last IMP application (see Section 10). They will also be asked to return at Week 6 for a primary endpoint visit (see footnote d). In addition, all subjects will have a final safety follow-up visit 2 weeks after last application of IMP.

- d) The primary endpoint visit is applicable to subjects who discontinue IMP prior to Week 6. The visit should be scheduled 6 weeks after the first application of IMP.
- e) The informed consent form(s) must be signed prior to performing any protocol-related procedures, including but not limited to screening evaluations and wash-out of disallowed medications.
- f) Medical history is to be recorded at screening. At baseline (Day 1), medical history for the selected target lesions is to be reviewed and updated, if needed (see Section 11.2.3).
- g) A full, global CLASI/RCLASI assessment will be done at screening. In addition, if any of the (potential) target lesions are located in the scalp, scarring alopecia will be scored for each scalp (potential) target lesion at screening and baseline to evaluate exclusion criterion no. 3.
- h) At screening, 2 potential target lesions will be identified and evaluated. At baseline (Day 1), the eligibility of the target lesions will be confirmed prior to randomisation. In the unlikely event that 1 or both lesions are no longer eligible at baseline, the investigator is allowed to select new target lesions if available (see Section 11.2.8).
- i) Investigator assessments of efficacy must be done prior to or at least 2 hours after application of IMP.
- j) In addition, the urine sample will be tested for proteinuria with a urine dipstick at screening (see Section 11.4.4).
- k) Non-invasive skin sampling must be done prior to or at least 4 hours after application of IMP.
- l) This procedure is optional and requires that the subject provides additional informed consent.

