### **11.2.7 Revised Cutaneous Lupus Erythematosus Disease Area and Severity Index**

The RCLASI is a revised, validated version of the CLASI (see Section 11.2.6). As the CLASI, the RCLASI is a tool to assess disease activity and damage in patients with CLE, taking both anatomical region and morphological aspects into account (Appendix 8) (28). In addition to erythema and scaling/hyperkeratosis, the RCLASI scores disease activity by oedema/infiltration and subcutaneous nodules/plaques. Mucous membrane lesions, non-scarring alopecia, and 'lupus hair' are also scored. Damage is scored in terms of dyspigmentation, scarring/atrophy, and scarring alopecia. The RCLASI score is the sum of the total activity and damage scores which are calculated by simple addition of the subtotals. A high RCLASI score indicates more severe disease.

At screening, the subjects will be scored according to the CLASI and RCLASI for a global disease assessment. The investigator will score all the elements according to the eCRF. To ease data collection, overlapping elements will only be recorded once.

At all subsequent scheduled visits, only the elements concerning skin lesion activity and damage will be assessed for each of the target lesions (see Sections 11.3.2 and 11.3.3).

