**Panel 9: Investigator's Global Assessment for discoid lupus erythematosus**

| Score | Disease severity | Morphological description  |
|-------|------------------|--|
| 0     | Clear.           | No activity signs of DLE (no erythema, no scaling/hyperkeratosis, no oedema/infiltration). Damage signs may be present (dyspigmentation and/or scarring/atrophy).  |
| 1     | Almost clear.    | Pink or faint erythema only. No scaling/hyperkeratosis, no oedema/infiltration.  |
| 2     | Mild.            | Pink or faint erythema. Slight scaling (mostly fine scales) and/or slight dermal oedema.   |
| 3     | Moderate.        | Prominent erythema. Slight scaling (mostly fine to circumscribed adherent scales) and/or slight to definite dermal oedema.   |
| 4     | Severe.          | Prominent red, dark red, purple, or violaceous colour. Crusting may be present. Severe scaling with follicular plugging and/or dermal oedema with skin induration. |

Abbreviation: DLE = discoid lupus erythematosus.

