**11.3.2 Skin lesion activity**

The assessment of skin lesion activity and skin lesion damage (Section 11.3.3) are based on the CLASI and RCLASI scoring scales for relevant disease signs (see Sections 11.2.6 and 11.2.7). The investigator will assess each target lesion for skin lesion activity at the visits indicated in the schedule of trial procedures (Section 4). The total skin disease activity score is defined as the sum of scores for erythema, scaling/hyperkeratosis, and oedema/infiltration.

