## **11.5 Pharmacodynamics and biomarkers**

### **11.5.1 Overview**

The pathogenesis of DLE is characterised by an inflammatory infiltrate localised in the dermis with presence of plasmacytoid dendritic cells and T cells. At the molecular level, the inflammatory response is dominated by type I and type II interferons and the chemokines CXCL9, CXCL10, and CXCL11, which are hallmarks of Th1 responses.

As an exploratory component of this trial, non-invasive skin samples and skin biopsies will be collected to create a general molecular profile of DLE and investigate how this profile changes upon treatment with delgocitinib. By comparing the expression of relevant biomarkers at the skin surface level (where drug exposure will be high) with changes across the whole skin depth in biopsies, it will be estimated to which extent the drug exposure in the dermis has been able to inhibit the pathogenic processes.

At all visits from baseline until end of treatment, non-invasive skin samples will be taken by applying a patch to the skin surface to absorb soluble material from the skin (see Section 11.5.2). After the trial, these patches will be analysed for disease-relevant cytokines and chemokines at the protein level. If no clinically relevant response to delgocitinib is seen, only patches from the baseline and end of treatment visits will be analysed.

Skin biopsies will be obtained at the end of treatment visit (Week 6) to analyse differences in gene expression (Section 11.5.3). Due to the invasive nature of this procedure, biopsies will be optional for the subjects. A focused panel of inflammatory and disease-related genes will be analysed by quantitative polymerase chain reaction (qPCR). A general expression analysis by microarray will be performed only if a clinically relevant response to delgocitinib is seen and if a sufficient number of biopsies is obtained to do a meaningful analysis.

Collection, handling, and shipment instructions for skin samples are provided in a separate laboratory manual. For subjects who do not complete the trial, the biopsies and non-invasive skin samples listed for Week 6 should be taken at the early termination visit.

A summary of the results will be included in the clinical trial report (CTR) if available at this time. The full results from the pharmacodynamics/biomarker analysis of all skin samples will be described separately in an addendum to the CTR.

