## **11.6 Other assessments**

### **11.6.1 Subject assessments**

#### **11.6.1.1 Patient's Global Assessment**

Subjects will assess the disease severity of each target lesion using the PaGA at the visits specified in the schedule of trial procedures (Section 4). The assessment will be made using the 5-point scale:

- 0 = Clear.
- 1 = Almost clear.
- 2 = Mild.
- 3 = Moderate.
- 4 = Severe.

The assessment will be based on the severity of the DLE lesions at the time of the assessment (and not in relation to the severity at previous visits). The PaGA should be completed before the investigator's assessments and without the investigator or site staff discussing the severity of the target lesions with the subject. The investigator will explain the categories of the scale to the subject who will then indicate which category should be ticked.

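### At the Week 6 primary endpoint visit for subjects who stop IMP early, Panel 2 schedules IGA but not skin lesion activity, damage or PaGA, so the FAS sensitivity analyses of 12 efficacy endpoints gain few or no early discontinuers

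*Combined protocol and SAP*

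**What the plan says.** Footnote d to Panel 2 defines the visit: "The primary endpoint visit is applicable to subjects who discontinue IMP prior to Week 6", and "The visit should be scheduled 6 weeks after the first application of IMP". In its column the IGA row is marked. The row beginning "Skin lesion activity (erythema, scaling/hyperkeratosis, oedema/infiltration" is not, nor are the rows for skin lesion damage and PaGA. All four rows are marked at Week 6, early termination and follow-up.

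The text leaves the choice of visits to that table. Section 11.3.2 states: "The investigator will assess each target lesion for skin lesion activity at the visits indicated in the schedule of trial procedures". Section 11.3.3 does the same for damage. Section 11.6.1.1 says of PaGA: "Subjects will assess the disease severity of each target lesion using the PaGA at the visits specified in the schedule of trial procedures". Section 10.3 refers to Section 4 for what is collected at the visits after IMP discontinuation.

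On the analysis side, Section 14.2 puts all randomised subjects in the FAS and removes from PP those who do not complete up to and including the Week 6 visit. Sections 14.3.5 and 14.3.6.1 make PP the primary set for the secondary and exploratory efficacy endpoints and repeat each analysis on the FAS as a sensitivity analysis. Section 14.3.12 assumes missing at random, without imputation.

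**The concern.** A main reason to repeat a PP analysis on the FAS is to bring back subjects who left treatment. Here the protocol calls those subjects back at Week 6 and grades their lesions by IGA, but does not schedule the scores that most of the other efficacy endpoints need. McNemar's test and the Wilcoxon signed rank test both work on within-subject pairs. Without Week 6 scores, the subject's pair drops out of the analysis.

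The loss may be selective. Lack of efficacy is a listed reason for stopping (Section 10.1), and unacceptable worsening of DLE requires IMP to be stopped (Section 10.2.1). The documents do not show which way this would move the comparison: a subject may stop because the vehicle lesion worsens, or because neither lesion improves.

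For skin samples the protocol provides a replacement when a subject does not complete: "the biopsies and non-invasive skin samples listed for Week 6 should be taken at the early termination visit". It states none for the clinical scores. A SAP finalised later, as Section 14.3.11 foresees, cannot supply scores that were never taken.

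**Working it through.** **1. Schedule cells (Panel 2)**

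| Row | Week 6 | Early termination | Primary endpoint visit | Follow-up (Week 8) |
|---|---|---|---|---|
| IGA | X | X | X | X |
| Skin lesion activity | X | X | blank | X |
| Skin lesion damage | X | X | blank | X |
| PaGA | X | X | blank | X |

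The adverse event and end of trial form rows also have an entry in the primary endpoint column, so the blanks are not a column lost in reading the table.

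**2. Endpoints affected (Panel 3)**

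- Efficacy secondary, 4 in all. The ≥2-point IGA reduction uses IGA. The ≥2-point erythema reduction, the erythema score and the total activity score need activity. Affected: 3 of 4.
- Clinical exploratory, 10 in all. One uses IGA, 2 need activity (scaling/hyperkeratosis, oedema/infiltration), 3 need damage (dyspigmentation, scarring/atrophy, total damage), 1 needs both (total lesion disease score) and 3 need PaGA. Affected: 2 + 3 + 1 + 3 = 9 of 10.
- Total: 3 + 9 = 12.

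**3. Subjects affected (Section 14.1)**

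The plan's own figure reproduces: 36 / (1 − 0.20) = 45 randomised. Expected drop-outs are 45 × 0.20 = 9. The documents do not split these into subjects who stop IMP but return at Week 6 and subjects who are lost, so the range is 0 to 9. If all 9 returned, the FAS could hold up to 45 pairs for the IGA endpoints at Week 6, against 36 completers.

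**4. How many could have a score by coincidence**

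Let t be the last IMP day, counted from first application. The Week 6 window is day 42 ± 3, that is days 39 to 45. Follow-up is at t + 14 ± 3, and Section 10.3 lets it share a day with the primary endpoint visit when both windows are met. The documents give no stopping times. For illustration, assume t is uniform over days 1 to 41 and all 9 keep attending.

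- Follow-up exactly 14 days after last IMP: 39 ≤ t + 14 ≤ 45 gives t = 25 to 31, 7 days. 9 × 7/41 = 1.5 subjects.
- Full ±3-day use of the follow-up window: t + 17 ≥ 39 and t + 11 ≤ 45 give t = 22 to 34, 13 days. Early termination on days 39 to 41 adds 3 days. 9 × 16/41 = 3.5 subjects.
- If nobody stops on those days, or those who do are not seen in the window: 0 subjects.

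So for the 12 endpoints the FAS would recover about 0 to 3.5 of the 9.

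**The case against.** The strongest reply is that the visit is deliberately minimal. It is named for the primary endpoint, and it also omits lesion size, vital signs and laboratory tests. That is a legitimate choice for people who have stopped treatment. But the protocol gives no reason for it and still plans FAS analyses of the endpoints it leaves uncollected.

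Second, discontinuers' scores are not lost altogether: activity, damage and PaGA are taken at early termination and at follow-up. This stands. Their condition at stopping can be described, but it is a Week 6 value only by coincidence of timing.

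Third, the consequence is small. PP is the primary set, every test is descriptive, and the FAS also restores subjects excluded from PP for other reasons, such as use of the wrong IMP. All of this stands and limits the point to a modest improvement.

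Fourth, Section 10.3 asks subjects who withdraw from the trial only for an early termination visit, so the change might not reach them. However, footnote c to Panel 2 asks both discontinuers and withdrawers to return at Week 6. How many would come is unknown.

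Two stronger readings should not be drawn. A reader might see a contradiction with Section 11.2.7: "At all subsequent scheduled visits, only the elements concerning skin lesion activity and damage will be assessed for each of the target lesions". That sentence goes on to point to Sections 11.3.2 and 11.3.3, both of which defer to Panel 2. It explains that the full indices are replaced by lesion scores after screening and does not add visits. A reader might also try to convert the Week 6 IGA into the missing scores, or to prove from Panel 9 that this fails at particular grades. The documents define no such mapping. For instance, Panel 9 describes mild disease with mostly fine scales, while the scaling scale in Section 11.3.2 has no level for fine scales. The point does not need the mapping.

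**Conclusion.** The point holds as a cheap improvement. Under Panel 2 as written, the FAS sensitivity analyses of 12 efficacy endpoints (3 secondary, 9 exploratory) add few or no early IMP discontinuers: at most 9 of 45 randomised are concerned, and possibly 0. It would be too strong to say that none can be added or that FAS and PP coincide, because visits can fall together and PP has other exclusions.

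Nor is the primary result affected. The primary endpoint and the ≥2-point IGA reduction have their Week 6 assessment scheduled for discontinuers, and the PP analyses do not change.

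This rests on the planned 20% drop-out, on reading the PP completion criterion as removing early stoppers, and, for the 0 to 3.5 figure only, on the illustrative stopping times and attendance above.

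**What to change.** In Panel 2, mark skin lesion activity at the primary endpoint visit. For the exploratory endpoints, also mark skin lesion damage and PaGA. Use these scores as the Week 6 values in the FAS analyses.

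If the sponsor wants to limit the addition, activity alone serves 3 + 2 = 5 of the 12 endpoints, including all 3 secondary ones. Activity plus damage serves 5 + 3 + 1 = 9, and PaGA the remaining 3.

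The cost is an amendment to the schedule and eCRF across approximately 20 sites, plus brief scoring of two lesions that the investigator already grades for IGA at that visit and, for PaGA, one subject rating per lesion. No visit is added. The change helps only subjects whose Week 6 visit is still to come.

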## 5 Introduction and trial rationale

### 5.1 Discoid lupus erythematosus

Discoid lupus erythematosus (DLE) is an autoimmune disease affecting the skin with erythematous, scaly, well-demarcated lesions. Over time, these lesions can cause scarring, atrophy, dyspigmentation, and hair loss, resulting in significant disfigurement. DLE lesions generally range in size from a few mm to 15 cm in diameter and are primarily found in ultraviolet (UV)-exposed areas such as the head and neck, and to a lesser extent on the trunk and extremities (1). The physical appearance affects the quality of life in DLE patients and is associated with increased risk of depression and unemployment (2).

DLE is one of the manifestations of lupus erythematosus (LE) which covers different disease types ranging from cutaneous to systemic involvement. In systemic LE (SLE), multiple organs including the heart, kidneys, skin, and joints may be involved. Cutaneous LE (CLE) can be either acute, subacute, or chronic, and DLE is the most common form of chronic CLE, representing 80% of all cases (2). The CLE disease types present with different clinical, histological, and serological features, and different prognoses (3).

The prevalence of CLE was estimated to 73/100.000 in an American study with a predominately white population (4). However, other studies have shown that DLE is more common in people with black skin (2, 5). DLE has a female predominance and a peak age of onset in the fourth decade in women and slightly later in men (6). DLE is categorised as either localised (only lesions above the neck) or generalised (lesions both above and below the neck), of which the localised form is far more common (7). Patients with generalised DLE are more likely to develop SLE than patients with localised DLE (8). In a Swedish cohort study, the probability for DLE patients to subsequently develop SLE was 16.7% after 3 years (9). Conversely, DLE develops during the course of SLE in 15-30% of SLE patients (10). DLE might progress to SLE more commonly in children than in adults (11).

The disease mechanism of DLE involves damage of the keratinocytes induced by UV sun light and the subsequent generation of autoantigens. This induces an inflammatory response resulting in characteristic histological features (12-14). The early inflammatory mediators include tumour necrosis factor alpha (TNF- $\alpha$ ) and interleukin (IL)-1 $\beta$  which attract skin-homing T cells and plasmacytoid dendritic cells (12, 13). Exposure to the autoantigens stimulates the production of interferon alpha (IFN- $\alpha$ ) and interferon gamma (IFN- $\gamma$ ) and further infiltration and activation of T helper (Th1) cells, which in turn activates the janus kinase (JAK)/signal transducer and activator of transcription (STAT) signalling pathways (15-17). The lesional tissue shows elevated levels of IFN- $\gamma$  and chemokines including chemokine

(C-X-C motif) ligand (CXCL) 9, CXCL10, and CXCL11, and an increased number of autoreactive cytotoxic cluster of differentiation 8 (CD8) positive T cells (12, 15, 16). In summary, the inflammatory disease profile indicates that the JAK/STAT pathway is central for the DLE disease mechanism and may be an important therapeutic target (18).

There is currently no cure for DLE, and no treatments have been approved for this indication. The current standard-of-care treatments are used off-label and have limited effect. First-line treatment recommendations include sun avoidance, UV protection, and potent topical corticosteroids. Topical calcineurin inhibitors are also used. In severe or widespread disease, systemic antimalarials are recommended (19).

## 5.2 Experience with investigational medicinal product

The investigational medicinal product (IMP) in this trial is delgocitinib cream.

Delgocitinib (recently assigned as the international non-proprietary name [INN] for LEO 124249) is a pan-JAK inhibitor. Delgocitinib blocks several cytokine-mediated signalling pathways and widely suppresses the activation of immune and inflammatory cells such as T cells, B cells, mast cells, and monocytes activated by these cytokines.

DLE is a new indication for delgocitinib, and no non-clinical or clinical data are available specifically for this indication. Current knowledge is mainly derived from clinical trials with delgocitinib ointment in the indications atopic dermatitis (AD) and chronic hand eczema (CHE). A compilation of non-clinical and clinical data for delgocitinib is given in the current version of the investigator's brochure.

CCI

A large section of the document is redacted with black bars. The redaction covers approximately six lines of text, starting from the 'CCI' label and extending down to the paragraph about clinical trials.

No clinical trials have yet been completed with delgocitinib cream. A total of 8 clinical trials (1 with delgocitinib oral formulation and 7 with delgocitinib ointment) were completed at the cut-off date for the investigator's brochure (version 2.0).

The efficacy of delgocitinib ointment was investigated in 6 trials in different indications (AD, CHE, inverse psoriasis, and alopecia areata) and was proven to be efficacious in AD and

CHE. Based on non-clinical dermal absorption studies, it is expected that delgocitinib cream will also be efficacious in these indications.

CCI [REDACTED]

